11.2.1.2. Unexpected Adverse Events and Unexpected Suspected Drug Reaction

An AE or suspected adverse reaction (an AE where there is a reasonable possibility that the drug caused the event; suspected drug related) is considered "unexpected" if it is not listed in the investigator brochure or is not listed at the specificity or severity that has been observed.

11.2.1.3. Serious Adverse Event

An SAE is any adverse event that occurs irrespective of study treatment assignment, if it satisfies any of these criteria:

- results in death;
- is life-threatening;

- requires inpatient hospitalization or prolongs existing hospitalization;
- results in persistent or significant disability or incapacity or substantial disruption of the ability to conduct normal life functions;
- is a congenital anomaly or birth defect;
- is an important medical event that, based upon appropriate medical judgment, may jeopardize the patient or subject and may require medical or surgical intervention to prevent one of the outcomes listed above.

11.2.2. Recording Adverse Events

Subjects will be encouraged to spontaneously report any changes in health from the time of informed consent signing through completion of the study. Study staff will also inquire about any changes in the subject's health.

All AEs will be recorded in the source document and the CRF. It is the responsibility of the Investigator to review all documentation (e.g., hospital progress notes, laboratory, and diagnostics reports) for the presence of AEs and for a complete evaluation of known AEs.

At minimum for each AE, the investigator will evaluate and report the event name/term/description, onset (date and time), resolution (date and time), event severity/intensity, relationship to study drug, action taken in regards to study drug, whether the event is an SAE, and whether or not it caused the patient to discontinue the study. The event time is only required while the subject is in the clinic.

11.2.2.1. Adverse Event Term/Name/Description

The Investigator will attempt to establish a diagnosis of each AE based on signs, symptoms, and/or other clinical information. In such cases, the diagnosis will be the AE term used to document the AE/SAE and not the individual signs/symptoms.

11.2.2.2. Relationship to Study Drug

The Investigator is obligated to assess the relationship between study drug and the occurrence of each AE/SAE. The Investigator will use clinical judgment to determine the relationship. Alternative causes, such as natural history of the underlying diseases, concomitant therapy, other risk factors, and the temporal relationship of the event to the study drug will be considered and investigated. The Investigator will also consult the Investigator's Brochure and/or Product Information for marketed products in the determination of his/her assessment.

The Investigator will assess causality as to whether the event is related or not related to study drug based on the following definitions:

- Not Related (If no valid reason exists for suggesting a relationship to study drug or the AE was more likely explained by causes other than study drug).

Study: SEL-212/201 Version: 7.1	Effective Date March 19, 2018
------------------------------------	----------------------------------

- **Unlikely to be Related:** Onset of the event has a reasonable temporal relationship to study drug administration and although a causal relationship is unlikely, it is biologically plausible.
- **Possibly Related:** Onset of the event has a strong temporal relationship to administration of the study drug and a causal relationship is biologically plausible
- **Related** (the study drug dosing and AE were closely related in time and the AE may be explained by exposure to study product: e.g., known pharmacological effect or recurrence on re-challenge).

There may be situations, particularly when an SAE has occurred, where the Investigator has minimal information to make an assessment in an initial SAE report. However, it is very important that the Investigator always make an assessment of causality for every SAE prior to transmission of the SAE report. The Investigator may change his/her opinion of causality in light of follow-up information, amending the SAE report accordingly. Any assessment of causality made by the Investigator should also be documented in the subject’s source medical record.

11.2.2.3. Adverse Event Intensity/Severity Grading

AEs will be classified according to the Rheumatology Common Toxicity Criteria, version 2.0 (Woodworth et al. 2007). The general framework for grading AEs is provided below, and the full scale is provided in Section 19.1 of the protocol.

- **Grade 1 (mild)** AE that is usually transient of short duration; or involves mild or minor symptoms which are of marginal clinical relevance; or is asymptomatic consisting of clinical or diagnostic observations alone; no intervention or only minimal treatment with non-prescription intervention was required. The event does not generally interfere with usual activities of daily living.
- **Grade 2 (moderate)** AE that is usually alleviated with additional specific therapeutic intervention. The event interferes with usual activities of daily living (e.g., shopping, laundry, transportation, or ability to conduct finances), causing discomfort but poses no significant or permanent risk or harm to the subject.
- **Grade 3 (severe)** AE that is medically significant/important but not life-threatening; may require brief hospitalization to prevent the event from worsening; interrupts usual activities of daily living, or significantly affects clinical status, or may require intensive therapeutic intervention.
- **Grade 4 (life-threatening)** An AE, and/or its immediate sequelae, which is associated with an imminent risk of death or which is associated with physical or mental disabilities that affect or limit the ability of a person to perform activities of daily living (eating, ambulation, toileting, etc.); disability may be persistent or result in significant disability, incapacity or limitation of self-care activities.

For an assessment of anaphylaxis, the clinical criteria for the diagnosis of anaphylaxis will be based on the National Institute of Allergy and Infectious Diseases (NIAID)/ Food Allergy & Anaphylaxis Network (FAAN) Symposium criteria for anaphylaxis diagnosis (Section 19.2).

11.2.2.4. Assessment of Outcome

The result or conclusion of the adverse event will be assessed and recorded by the Investigator as:

- Fatal
- Not recovered/not resolved (the AE has not improved or subject has not recuperated).
- Recovered/resolved (the AE has improved or subject has recuperated)
- Recovered/resolved with sequelae (recuperated but retained pathological conditions resulting from the AE)
- Recovering/resolving (the subject is improving but the AE has not yet resolved)
- Unknown (not known, not observed, not recorded, or refused)

11.2.2.5. Action taken with study drug

The action taken in regards to study drug will be assessed by the investigator as:

- Dose not changed (dose completed)
- Dose reduced (IV infusion was modified by subtraction by changing the amount dosed)
- Dose interrupted (IV infusion was temporally modified by temporarily stopping the infusion; slowing of the rate of infusion should also be classified as interrupted)
- Drug withdrawn (IV infusion was modified through termination of the infusion)

A response option for increasing the dose is not an available course of action in this study.

11.2.2.6. Laboratory and Diagnostic Abnormalities as Adverse Events

Clinically significant abnormal laboratory findings or other abnormal diagnostic assessments (e.g., ECGs, vital signs) that are detected in dosed subjects or that significantly worsen relative to baseline in dosed subjects will be reported as AEs or SAEs. Clinically significant is based on investigator judgment but will typically include findings that results in study withdrawal, result in active management of the subject, or are associated with clinical signs and symptoms. Since the study requires subjects with elevated or abnormal uric acid levels, abnormal uric acid levels will typically not be an AE unless judged by the Investigator as being more severe than expected for the subject.

11.2.2.7. Pregnancy

While pregnancy itself is not considered to be an AE or SAE, any pregnancy complication or elective termination of a pregnancy for medical reasons will be recorded as an AE or a SAE and followed. The outcome of all pregnancies must be followed up and documented even if the subject is no longer a study participant.

The Investigator, or his/her designee, will collect pregnancy information on every female who becomes pregnant while enrolled in this study and on every female partner of a male subject who becomes pregnant while the male partner is enrolled in this study. The Investigator will report to the Sponsor or Sponsor's designee within 24 hours of learning of a subject's or female partner of a subject's pregnancy. The subject or female partner of a subject must also be followed to determine the outcome of the pregnancy. Information on the status of the mother and child will be forwarded to the Sponsor or Sponsor Designee, as appropriate. Follow-up on the child will be to the first well-child visit. Any premature termination of the pregnancy will be reported.

A spontaneous abortion, congenital abnormalities/birth defects will be considered SAEs and will be reported as such. Furthermore, any SAE occurring as a result of a post-study pregnancy and is considered reasonably related to the study drug by the Investigator, will be reported to the Sponsor.

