Oligo/azoospermia has been seen in some male renal transplant patients taking an oral form of SEL-110 (rapamycin) administered chronically on a daily or three times weekly basis for the prevention of transplant rejection when treated for a period greater than six months. The mechanism for this effect is not known. In those patients where oligo/azoospermia has been seen partial to full reversibility of sperm production following cessation of treatment with the oral form of rapamycin has been demonstrated (e.g., Deutsch et al., 2007; Skrzypek, 2007; Zuber et al., 2008). Male patients should be informed that their fertility may be affected temporarily or permanently after being given SEL-110.

In preclinical animal studies performed with an oral form of the drug to be administered in this study, SEL-110 (a component of SEL-212) showed adverse effects when given to pregnant rats. These effects included fetal death, reduced fetal weights, and delays in the formation of bones. It is not known whether these effects would also occur humans, a similar risk should be considered possible until such studies are performed. Because of these potential adverse effects, all females who directly participate in this clinical study must be of no childbearing potential and all males with female partners with childbearing potential must agree to use effective contraception and agree to continue doing so for four months after study drug dosing. Childbearing potential is defined as: a) less than 6 weeks after surgical removal of ovaries, tubes with or without removal of the womb or (b) pre or perimenopausal (less than 24 months of being without a period naturally).

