6.3.1. Stopping Rules in an Individual Subject or in a Cohort

For this clinical trial a treatment period is defined as period of time from the beginning of dosing of the first study drug on a given dosing day (ie, Either saline placebo or SEL-110 during Part A of the study and SEL-037 during Part B of the study) to the beginning of the next scheduled dose of study drug, and has a typical duration of 28 days.

For Part C (Cohorts 13, 15, and 17), a treatment period is defined as the period of time from the beginning of dosing of SEL-212 to the beginning of the next scheduled dose of study drug.

Individual

For subjects in Cohorts 1 and 2, any subject who has a weekly serum uric acid value ≥ 6 mg/dl or $>50\%$ of their baseline (where baseline value refers to the pre-dose serum uric acid level from visit 4, Day 0, treatment period 1) at Day 21 of their current treatment cycle will not be eligible for the next dosing of SEL-037. The subject will be followed for 30 days post the last dose of study drug at which time they will have an End of Study assessment and their participation in the study will be terminated.

In Cohorts 3-8, 10-13, 15, and 17 only subjects whose ambient blood samples indicate a serum uric acid (sUA) value less than or equal to 1.0 mg/dL at any of the Day 21 visits will be eligible for the next dosing of SEL-212 (or SEL-037). All other subjects will be followed for 30 ± 2 days post the last dose of study drug at which time all of the End of Study assessments will be completed and their participation in the study will be terminated.

Cohort

If 5 subjects in any of Cohorts 1-5 or 7, or if 10 subjects in any of Cohorts 6, 8, 10, 11, or 12 have met the requirements for individual stopping of their participation in the trial as described above or have been stopped based on Section 6.4 then that cohort will no longer have any additional subjects enrolled in it. Those subjects who have been enrolled will continue until they fulfill the requirements

Study: SEL-212/201 Version: 7.1	Effective Date March 19, 2018
------------------------------------	----------------------------------

for individual stopping or complete the clinical trial treatment periods. If they continue to meet the requirements for continued participation they may continue in Part B of the study.

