6.4. Criteria for Study Termination

The study will be terminated when the subjects have completed follow-up assessments as per Section 1.1 or the medical monitor, Sponsor, Investigators, safety committee, IRB or regulatory agencies have determined there is an unacceptable risk to subjects or additional dosing or procedures are not warranted or necessary.

The study may be terminated at a particular investigational site under the following conditions:

- The Investigator fails to enroll subjects at an acceptable rate;
- The Investigator fails to comply with pertinent regulations;
- There is insufficient adherence to the protocol;
- Knowingly false information is submitted to the IRB, Sponsor or designee, or regulatory authorities;

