7.3.2. Contraception

Females must be of non-childbearing potential, where childbearing potential is defined as being: (a) <6 weeks after surgical bilateral salpingo-oophorectomy with or without hysterectomy or (b) pre or perimenopausal (< less than 24 months of natural amenorrhea).

All males with female partners with childbearing potential agree to use effective contraception and agree to continue doing so for four months after study drug dosing. Effective contraception is defined (for male subjects with a female partner with childbearing potential) as (a) two separate forms of contraception simultaneously, one of which must be a male condom with spermicide; or (b) be non-heterosexually active.

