7.3.4. Blood and Sperm Donations

Subjects will be advised that they should not donate blood and males should not donate sperm until after completion of this study.

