7.4.2. Subject Completion

A subject will be considered to have completed the study when the subject has completed the Treatment Period 5, Day 30 visit. Enrolled subjects who prematurely discontinue for any reason before completion of the study will be treated as outlined in the following section.

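### Male contraception runs for four months after dosing, but the stated duty to collect partner pregnancies ends with enrolment and the sperm-donation advice is not tied to the same period

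*Protocol*

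**What the plan says.** **Precaution.** Protocol 4.4.2 explains that rapamycin given orally "showed adverse effects when given to pregnant rats". It then requires males whose female partners could become pregnant to "agree to use effective contraception and agree to continue doing so for four months after study drug dosing". Section 7.3.2 repeats the requirement: such men must "agree to continue doing so for four months after study drug dosing". Section 9.1 lists both SEL-037 and SEL-110 as study drugs.

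**Collection.** Section 11.2.2.7 tells the investigator to collect pregnancy information "on every female partner of a male subject who becomes pregnant while the male partner is enrolled in this study".

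**Sperm donation.** Section 7.3.4 advises that "males should not donate sperm until after completion of this study".

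**End of participation.** Section 7.4.2 states: "A subject will be considered to have completed the study when the subject has completed the Treatment Period 5, Day 30 visit". Subjects who meet an individual stopping rule are followed for 30 days (30 ± 2 in the SEL-212 cohorts), "at which time all of the End of Study assessments will be completed and their participation in the study will be terminated" (6.3.1). Section 7.4.3.1 also uses 30 days after the last dose for subjects who stop early.

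**End of study.** Section 6.4 states: "The study will be terminated when the subjects have completed follow-up assessments as per Section 1.1".

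**Later contact.** Section 10.1.1 adds a visit 60 ± 1 days after the fifth dose for subjects whose uric acid is below 6 mg/dL at Period 5 Day 21. It lists blood samples only.

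**The concern.** The protocol sets a precaution of four months, but two rules that depend on it stop earlier or have no fixed end. A man can still be under the contraception requirement when the stated duty to record his partner's pregnancy has lapsed. If 7.3.4 refers to his own completion, he could donate sperm from about Day 31 while still required to use a condom with spermicide.

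Female subjects must be of non-childbearing potential, so a partner pregnancy is the main way this trial could produce human pregnancy information. Section 4.4.2 says a risk in humans should be considered possible until it has been studied. What is at stake is a small amount of safety information about third parties. The SAP is not affected: its primary safety endpoints (SAP 4.3) stop at 30 days after the last dose.

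The protocol also does not say which dose starts the four months. In Parts A and B the last SEL-110 infusion comes two periods before the last SEL-037 infusion, so the choice matters.

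**Working it through.** The documents give no figure for uncovered days, so there is none to reproduce. The check is calendar arithmetic.

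**Inputs**
- Contraception period: four months, taken as 120 days (four calendar months span 120 to 123 days).
- End of participation: 30 days after the last dose (7.4.2, 7.4.3.1, 6.3.1), with a window of ± 1 day for the End of Study visit or ± 2 days for stopped SEL-212 subjects.
- Optional visit: Day 60 ± 1 (10.1.1).
- Reference dose: the last dose of either product, because 9.1 calls both study drugs.

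**Partner pregnancies.** Days with no stated collection period = 120 − days from last dose to end of enrolment.
- Participation ends at Day 30: 120 − 30 = **90**. With ± 1 day, 89 to 91; with ± 2 days, 88 to 92. Calendar months add at most 3.
- Day 60 visit counted as enrolment: 120 − 60 = **60** (59 to 61), for attenders only.

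**Sperm donation**
- Subject's own completion (7.4.2): 120 − 30 = **90**.
- End of the study (6.4): let X be the days between this man's last dose and the last dose given to anyone. If the study ends 30 days after that final dose, the gap is max(0, 120 − (X + 30)) = max(0, 90 − X). This gives 90 at X = 0, 45 at X = 45, and **0** once X is 90 or more. If the final subject's Day 60 visit marks the end, it becomes max(0, 60 − X).

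**Sensitivity to the starting dose.** Doses fall on Days 0, 28, 56, 84 and 112. Suppose the four months ran from the last SEL-110 dose instead.
- SEL-212 completers in Parts A and B had that dose on Day 56 and finish on Day 142, which is 86 days later, so the gap is 120 − 86 = 34.
- Those stopped after dose 4 have 28 + 30 = 58 days covered and a gap of 62.
- Those stopped after doses 1 to 3, and Part C subjects who stay on SEL-212, remain at 90.

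This count departs from the wording of 7.3.2, so 90 is used as the main figure.

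**After the change.** With both rules running to four months after the last dose, the gap is 0.

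**The case against.** **Later pregnancies are not ignored.** A reader might infer that a partner pregnancy beginning after Day 30 falls outside the protocol altogether. The text does not support that. Section 11.2.2.7 has several clauses with no end date: a report within 24 hours of learning of a pregnancy, follow-up of every pregnancy outcome even after the subject has left, and spontaneous abortion and birth defects treated as SAEs. It also requires related SAEs from a post-study pregnancy to be reported, and 11.3.1 does the same for any related SAE learned of after discharge. This part of the objection stands: what is missing is a defined collection period, not all coverage. But these clauses work only if someone volunteers the news. The one sentence that names post-study pregnancy is limited to SAEs judged related, so a normal outcome, or an adverse one judged unrelated, is not clearly captured.

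**The periods need not match.** Contraception is prevention and collection is surveillance, and nothing in the documents requires them to be equal. The cited fetal findings come from dosing pregnant rats; 4.4.2 reports no effect transmitted through the father. Two contraceptive methods are required unless the man is not heterosexually active, so pregnancies should be few. All of this holds and keeps the point minor. It does not explain why sperm donation might resume while contraception is still required.

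**Unseen text.** The consent pages and Tables 1 and 5 are not in the available file, and an instruction to men could be there. That would help in practice, but 7.3.4 and 11.2.2.7 would still disagree with 7.3.2.

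**Timing.** Reports could arrive after a site has closed. This is a real cost and belongs in the fix.

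**Conclusion.** The mismatch is in the protocol text. On the literal reading, with participation ending at Day 30, about 90 of roughly 120 days have no stated period for collecting partner pregnancies. That becomes about 60 for Day 60 attenders if that visit counts as enrolment. For sperm donation the gap is about 90 days on the subject-level reading, and smaller or zero for earlier-dosed men on the study-level reading.

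These sizes assume a 120-day period, counting from the last dose of either product, and 30-day participation.

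Three stronger inferences are not supported:
- That paternal exposure has been shown to harm a fetus. Male contraception here is a precaution.
- That monitoring drops from active to passive at Day 30. The visible schedules contain no pregnancy question during enrolment either.
- That the number of new subjects affected is capped at the places now open in Cohorts 11 and 12 and Part C. Section 6.2 allows closed cohorts to be re-opened, and the documents do not say how many subjects are men with partners of childbearing potential.

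Severity is minor. No planned analysis, sample size or error rate is affected.

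**What to change.** 1. In 11.2.2.7, replace the enrolment limit for partners with a period from first dose through four months after the last dose of study drug, whatever causality is judged to be.
2. In 7.3.4, end the sperm-donation advice at four months after the last dose of study drug.
3. In 4.4.2 and 7.3.2, state that the four months run from the last dose of either study drug.
4. At the End of Study or Early Termination visit, tell male subjects to report any partner pregnancy in that period, and say who receives reports once a site has closed. For those who attend the Day 60 visit, one question there would be a cheap addition.

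**Cost.** Amendment wording in four sections (five if 10.1.1 gains the Day 60 question), with the IRB approval that 14.2 requires, and one instruction at an existing visit. The downside is light reporting for about three months past normal participation, and outcome follow-up to the first well-child visit, as 11.2.2.7 already requires, for the few pregnancies reported. Some of this may fall after site close-out. No table, endpoint or analysis set in the SAP needs to change.
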